### **Other analysis supporting the secondary (inc. sensitivity analyses)**

None

## **SAFETY AND TOLERABILITY ANALYSES**

Adverse event data will be summarised with descriptive statistics.

### **Intervention exposure**

The number of participants receiving medication will be summarised per treatment group.

All Adverse events

See table 7 in the appendix

Adverse events leading to withdrawal

See table 2 in the appendix

Serious adverse events

See table 8 in the appendix

Clinical laboratory evaluations

There are no AEs defined by laboratory evaluations

## **SUBGROUP ANALYSES**

### **Definition of outcome measure**

For each participant, the total number of unscheduled medical attendances over the course of the trial.

### **Definition of subgroups**

The primary analysis will be repeated to assess whether there is a differential effect of treatment by:

Genotype, categorised as 5/5 vs (5/x and x/x) and alternatively as (5/5 and 5/x) vs x/x

Whether ICS taken at baseline (yes,No)

Episodic vs multitrigger wheeze at baseline

### **Sample size justification for the subgroup analysis**

The study has been powered to detect a specific interaction effect.

### **Descriptive analysis for subgroups**

The mean and standard deviation of the number of unscheduled medical attendances will be summarised for each ALOX5 genotype and each treatment group

### **Method of analysis**

The primary analysis will be repeated including an interaction term between treatment and stratum. The significance of the interaction term assessed.

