#### **Secondary objectives**

2.To determine whether the effect of treatment on the primary analysis is different depending upon ALOX5 status (5/5 vs. 5/x and x/x).

3.To determine whether intermittent treatment with oral montelukast in preschool children reduces the time to first medical attendance.

4.To determine whether intermittent treatment with oral montelukast in preschool children reduces the need for each type of medical attention for wheeze: hospital admissions; hospital attendance; and GP visits.

5.To determine whether intermittent treatment with oral montelukast in preschool children reduces the time to first occurrence of each type of medical attention for wheeze: hospital admissions; hospital attendance; and GP visits.

6.To determine whether intermittent treatment with oral montelukast in preschool children reduces the duration of hospital admissions.

7.To determine whether intermittent treatment with oral montelukast in preschool children reduces the number of episodes, duration and time to first event of wheeze and cold.

8.To determine whether intermittent treatment with oral montelukast in preschool children reduces the need for alternative medications (Steroids, Salbutamol).

9.To describe the safety profile of montelukast.

10.To describe parents opinion of treatment efficacy

11.To describe compliance to medication

12.To determine whether baseline urinary eicosanoid level is different across baseline groups: ALOX5 status (A or B), leukotriene genes and, type of wheeze (episodic, multitrigger). **NOTE ANALYSIS DETAIL NOT CONTAINED IN THIS PLAN**

13.To determine whether montelukast is cost effective. **NOTE ANALYSIS DETAIL NOT CONTAINED IN THIS PLAN**

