### **Sample size determination**

This trial is powered to detect a clinically significant difference in the number of attacks of wheeze between intervention and control arms. We also had power to detect large differences responsiveness (in terms of the primary outcome) to montelukast in the stratum with ALOX5 promoter polymorphism [5/5], compared with the stratum with the ALOX5 [5/x and x/x]" genotype.

Data on mean (0.76) and standard deviation (1.22) of number of attacks come from data from the UK General Practitioner Research Database on courses of oral steroids (a proxy for number of episodes). These data follow an overdispersed Poisson distribution. To take account of this we used markov chain Monte Carlo simulation in WinBUGS to estimate sample sizes required: (WinBUGS Version 1.4. 2003 Available from: <http://www.mrc-bsu.cam.ac.uk/bugs/welcome.shtml>). To detect

a 33% drop in attack rate requiring medical attention, with a power of 90% and at a significance level of 5%, and a 6% loss to follow up, we require 1050 children in total. A 33% drop in attack rates equates to an attack rate of 0.51 for the treatment group. The clinical significance of these changes is that approximately four children will need to be treated to prevent one clinically severe attack. A sample size of 1200 gives just over 80% power at the 5% significance level to detect an interaction between treatment and genotype if the effect is a 60% reduction in the [5/x plus x/x] and a 20% reduction in the [5/5] stratum. Assuming a 6% dropout, 1300 children will need to be recruited.

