### **GENERAL ISSUES FOR STATISTICAL ANALYSIS**

All analyses will be conducted two sided and significance interpreted at the 5% significance level.

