### **Primary analysis**

The primary analysis will be a Poisson regression model with the follow up time of each individual fitted as an exposure variable and with a random effect for individual to account for overdispersion.

The incident rate ratio (IRR) for the treatment effect and corresponding 95% confidence interval will be presented. An IRR of less than 1 indicates a benefit of Montelukast in reducing the rate of unscheduled medical attendance needed.

Assumption checks and actions to be taken if assumptions do not hold

The fit of the model will be compared to a model without a random effect using the likelihood ratio test, and the fit will be assessed using diagnostic plots (residuals versus fitted values), alternative distributions to the Poisson such as the Negative binomial or removal of the random effect shall be considered where necessary for improved fit.

Other analysis supporting the primary (inc. sensitivity analyses)

The primary analysis will be performed on the per-protocol population and using a CACE analysis.

It will be repeated replacing any stratification factors that were incorrectly defined at randomisation with the corrected values (see section 1.4).

It will be repeated with exclusion of 11 incorrectly randomised participants (see section 1.4).

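### The ALOX5 interaction is fitted on 'stratum', and the plan does not say that it uses the corrected genotype

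*SAP*

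**What the plan says.** Objective 2 (SAP, Secondary objectives) asks whether the "effect of treatment on the primary analysis is different depending upon ALOX5 status". Definition of subgroups gives two genotype splits: "Genotype, categorised as 5/5 vs (5/x and x/x) and alternatively as (5/5 and 5/x) vs x/x". Descriptive analysis for subgroups also summarises by ALOX5 genotype.

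The model is set in Method of analysis: "The primary analysis will be repeated including an interaction term between treatment and stratum". The footnote to Table 3 likewise describes a treatment effect that depends on stratum, and the table has rows for Stratum A and Stratum B.

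On the wrongly assigned strata, the supporting analyses of the primary outcome say: "It will be repeated replacing any stratification factors that were incorrectly defined at randomisation with the corrected values". Other populations describes the matching analysis set. No visible section applies the corrected values to the interaction.

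Sample size determination states power for this interaction: "A sample size of 1200 gives just over 80% power at the 5% significance level to detect an interaction between treatment and genotype". The planning effects are rate ratios of 0.40 in the pooled non-5/5 group and 0.80 in the 5/5 group, which the same section words as "a 60% reduction in the [5/x plus x/x] and a 20% reduction in the [5/5] stratum".

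**The concern.** The corrected values are used where they matter least. Allocation is 1:1 in blocks of 10 within each stratum, so a few wrong values of an adjustment covariate hardly move the overall rate ratio. In a treatment-by-genotype interaction the same errors do matter. Each labelled stratum then contains some children of the other genotype, so the two rate ratios move towards each other.

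Stratum was assigned before allocation, so the errors should be unrelated to treatment arm and the expected direction is dilution. This is the one subgroup test for which the SAP states power, and the stated margin over 80% is small.

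The two genotype tests may also classify differently. The second split, x/x against the rest, cannot be read from the randomisation stratum, because Group II pools 5/x and x/x. It needs each child's genotype. If the first split uses the as-randomised label, a mis-stratified child could be classified by label in one test and by genotype in the other.

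**Working it through.** **Inputs from the SAP**
- Control mean 0.76 and SD 1.22 (Sample size determination: "Data on mean (0.76) and standard deviation (1.22) of number of attacks").
- Rate ratios 0.80 in 5/5 and 0.40 in 5/x plus x/x, so the true log interaction is ln(0.40/0.80) = −0.693.
- N = 1200, allocation 1:1, two-sided 5% ("All analyses will be conducted two sided and significance interpreted at the 5% significance level").

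**Assumptions, because the SAP gives no figure**
- A 5/5 share of 50% or 75%.
- The same control mean in both strata.
- An error rate e, equal in both directions.
- Negative binomial variance.

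**Formulas**
- Dispersion: k = (1.22² − 0.76)/0.76² = 1.261.
- Variance of a log rate in a cell with mean μ and n children: (1/μ + k)/n. The interaction variance V is the sum over the four treatment-by-stratum cells.
- Power = Φ(|log interaction|/√V − 1.96).

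**The plan's own figure.** At a 75% share there are 450 children per arm in 5/5 and 150 per arm in the other stratum. The terms 1/μ + k are:
- 2.577 for control (μ = 0.76)
- 2.906 for treated 5/5 (μ = 0.608)
- 4.551 for treated non-5/5 (μ = 0.304)

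V = (2.577 + 2.906)/450 + (2.577 + 4.551)/150 = 0.0597 and √V = 0.244. The ratio is 0.693/0.244 = 2.84, and power is Φ(0.88) = 81%. At a 50% share it is 92%. The stated figure is therefore plausible, but it cannot be confirmed without the share.

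**Adding misclassification, example at a 75% share and e = 5%**
- Labelled 5/5: 0.7125 true and 0.0125 false, so 98.3% are truly 5/5. The rate ratio becomes 0.983 × 0.80 + 0.017 × 0.40 = 0.793.
- Labelled non-5/5: 0.2375 true and 0.0375 false, so 86.4% are truly non-5/5. The rate ratio becomes 0.864 × 0.40 + 0.136 × 0.80 = 0.455.
- Log interaction: ln(0.455/0.793) = −0.557, which is 80% of −0.693.
- With cell sizes 435 and 165, √V = 0.231. The ratio is 2.41, and power is Φ(0.45) = 67%.

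**Range**

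| 5/5 share | e | Shrinkage of log interaction | Power |
|---|---|---|---|
| 75% | 0 | none | 81.0% |
| 75% | 0.8% | 4% | 78.9% |
| 75% | 2% | 9% | 75.7% |
| 75% | 5% | 20% | 67.3% |
| 50% | 0 | none | 92.2% |
| 50% | 0.8% | 2% | 91.4% |
| 50% | 2% | 4% | 90.0% |
| 50% | 5% | 11% | 85.8% |

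The 0.8% row is 11/1347. It uses the only count of randomisation errors in the visible text as a guide to scale. Those 11 form a separately described exclusion group, and the SAP does not say whether they are the mis-stratified children.

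A quasi-Poisson variance (1.22²/0.76 = 1.96 times Poisson) lowers the starting power to 73% and 88%. The losses stay similar: 2.1 and 1.1 points at 0.8% error, and 12.8 and 7.5 points at 5%.

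**The case against.** The strongest reply is that Method of analysis says only 'stratum' and not the stratum as randomised. The surrounding text points to genotype: objective 2 speaks of ALOX5 status, and the subgroup definition and the descriptive summary speak of genotype. Objective 12 attaches the labels A and B to ALOX5 status, so the Table 3 rows may be genotype labels. The word is also used loosely. Table 3 calls the second genotype split a stratum, the note to Table 1 calls it an alternative stratification, and the same method sentence has to serve baseline ICS use and wheeze type, which were never stratification factors. In addition, the primary analysis refers to a section 1.4 on these errors that is not in the visible text. Their number and handling may be set out there.

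Most of this stands. A reader might infer that the SAP lays down the as-randomised label as the rule for the interaction. It does not. That is the likelier reading of an ambiguous term, because the interaction repeats the primary analysis, and the primary analysis carries the uncorrected value (otherwise the corrected repeat would not be a sensitivity analysis). The different classification of one child in the two tests depends on the same reading.

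What the reply does not remove is that the visible text never says which value enters the interaction. Because the analysis is run unblinded, that should be fixed in advance.

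**Conclusion.** The point holds as an unresolved choice whose natural reading is the worse option. Followed as written, the genotype interaction and the Stratum A and B rate ratios most likely include values known to be wrong, and this biases the interaction towards the null.

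The probable size is modest. If errors are of the order of 0.8%, the log interaction shrinks by about 2% to 4% and power falls by about 1 to 2 points. Losses of about 6 to 14 points need an error rate of 5%, roughly 67 of 1347 children, and nothing in the visible text supports a rate that high. A reader might take the fall from 81% to 67% as the expected loss. It is the unfavourable end of an assumed range. All these figures rest on an assumed 5/5 share of 50% to 75%, symmetric errors and equal control rates in the two strata.

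The main treatment effect is not in question, and its corrected-stratum sensitivity analysis is already planned.

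**What to change.** In Descriptive analysis for subgroups, Method of analysis, and Table 3 with its footnote, state that both genotype interactions and all genotype-specific rate ratios use the corrected ALOX5 genotype. Report the interaction on the as-randomised stratum as a sensitivity analysis, and report how many children were mis-stratified and in which direction. Keep the as-randomised stratum as the covariate in the main-effect model.

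The cost is a change of wording and one extra model run. The corrected values are already planned for use. Genotype is fixed before treatment, so reclassifying a child leaves the randomised arms unchanged.

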### **AMENDMENTS TO VERSION X**

[figure not shown]

# Appendix: Statistical Analysis Report Template

## CONSORT Flow Diagram

PCTU\_SOP SP\_01 Associated document

Not to be used without prior permission by the PCTU.

Version 2.0

**Table 1: Baseline comparability of treatment groups**

ITT population	Montelukast			Placebo		
	5/5	5/x and x/x	Total	5/5	5/x and x/x	Total
Height (cm)						
Weight (Kg)						
Age (years)						
Gender						
	Male					
	Female					
Stratum						
	A					
	B					
Ethnicity						
	Asian or Asian British					
	Mixed					
	Black or Black British					
	White					
	Other					
Pre existing conditions						
	X					
	Y					
	Z					
Age at first wheeze (months)						
Interval between onset of URTI and wheezing (hours)						
Episodic wheeze						
Multi-trigger wheeze						
Admitted to hospital in last year						
Admitted to hospital ever						
Preventer therapy						
	None					
	Antileukotriene					
	Maintenance inhaled steroids					
	Episodic inhaled steroids					
Risk factors						
	Preterm birth <37 wk gestation					
	Birth weight <2500g					
	Food allergy					
	Drug allergy					
	Itchy rash for > 6 months					
	Eczema					
	Tobacco exposure in utero					
	Tobacco exposure in					

---

household  
 Daycare attendance  
 Immunised for  
 Pneumococcus  
 Immunised for influenza  
 History of asthma in  
 mother  
 History of asthma in  
 father

Numbers are N(%) or mean (SD)

This table is to be repeated for the alternative stratification (5/5 and 5/x) versus (x/x).

**Table 2: losses to follow up**

ITT population	Montelukast			Placebo		
	Trial	Treatment	Total	Trial	Treatment	Total
Reason for withdrawal						
Eligibility no longer met						
Death						
Other adverse event						
Deterioration of pre-existing condition						
Poor adherence to treatment						
Perceived lack of efficacy						
Unable to locate participant						
Other						
Decision made by						
CI						
PI						
Referring investigator						
Carer						
Participant						
Other						
Permission to use data						
Do not use any data						
Use partial data up to withdrawal						
Use all data up to withdrawal						
Collect and use all follow up data						
Numbers are N (%)						

**Table 3 Primary analysis: unscheduled medical attendances for wheeze over 12 months**

ITT population	Montelukast N=	Placebo N=	Adjusted IRR (95% CI) 	p-value
Follow up time (days)				
Number of :				
Any medical attendance				
All				
Stratum A				
Stratum B				
Stratum 5/5 and 5/x				
Stratum D x/x				

ICS at baseline  
Multitrigger vs episodic wheeze

**Hospital admissions**  
**Hospital attendances (A&E or admission)**  
**Unscheduled GP visits**

**Parents considered medication to be efficacious, N(%)**

---

Data are mean (SD)

 Data are analysed using Poisson regression with fixed effects for stratification factor and treatment group a random effect for individual to account for overdispersion with follow up time fitted as the exposure. An interaction term has been included to assess whether there is a differential treatment effect dependent on stratum.

**Table 4: Episodes of cold and wheeze**

---

ITT population	Montelukast N=	Placebo N=	IRR (95% CI) 	p-value
----------------	-------------------	---------------	---------------------------	---------

---

**Number of:**  
**Wheeze episodes**  
**Cold episodes**  
**Days wheezing**  
**Returned used medication sachets**

**Duration of:**  
**Wheeze episodes (days)**  
**Hospital admission (days)**

---

Data are mean (SD)

 Data are analysed using Poisson regression with fixed effects for stratification factor and treatment group a random effect for individual to account for overdispersion with follow up time fitted as the exposure. Duration of each hospital admission is analysed using Poisson regression with fixed effects for stratification factor and treatment group a random effect for individual with follow up time fitted as the exposure.

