**Description of wheezing episodes**

Wheeze:

- Number of wheeze episodes\* as recorded on the diary card
- Time to first episode\* of wheeze as recorded on the diary card
- Duration of wheeze episodes\* as recorded on the diary card

Cold

- Number of cold episodes\* as recorded on the diary card
- Time to first episode\* of cold as recorded on the diary card
- Duration of cold episodes\* as recorded on the diary card

**\*Definition of episode of wheeze and cold: The duration of an episode is defined as the days from the start of symptoms until the last days of symptoms (includes both start and stop day) followed by a period of 5 symptom free days.**

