### ***Withdrawals***

Withdrawal (from treatment or trial)

Date of withdrawal

Reason for withdrawal (eligibility no longer met, death of participant, other adverse event, deterioration of pre-existing condition, Poor adherence to treatment, Perceived lack of efficacy, unable to locate participant, other)

Withdrawal decision by (CI, PI, Referring investigator, Carer, Participant, other)

Permission to use data (do not use any data, use partial data up to withdrawal, use all data up to withdrawal, collect and use all follow up data)

Code broken (Yes/No)

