### **Method for handling non-adherence**

Analysis of all primary and secondary outcomes will be performed on an intention-to-treat basis. A Complier Average Causal Effect (CACE) analysis and per protocol analysis will also be conducted for the primary analysis.

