## **Derived and computed variables**

All derived and computed variables will be documented in the analysis programmes. The primary outcome is a summation of all types of medical attendances across the entire trial, for each participant.

The primary outcome, and the breakdown of unscheduled medical opinion, will be taken solely from the phone call data as this data has been confirmed against clinical records.

Medication use data may be recorded on either the phone call CRF and/or the diary card. A medication will be defined as being used if it appears in either of these two records.

Medical attendance data was collected strictly within 12 months, as calculated from the date of randomisation. Participants who do not experience an event are censored at exactly 12 months of follow up or the point of withdrawal from follow up. Any diary data collected outside of the 12 month follow up will be excluded from the analysis. Participants who do not experience episodes of cold or wheeze will be censored at the point of 12 months from randomisation or withdrawal from medication, as diary cards are not completed for those not taking IMP.

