### **Secondary analysis**

The primary analysis will be repeated for each of the following secondary outcomes:

individual type of medical attendance: (hospital admission, hospital attendance (a&e), and GP visit)

Duration (in days) of hospital admission

Number of wheeze episodes

Duration of wheeze episode

The number of steroid (OCS) courses per year

The number of IMP courses per year

Time to event data will be summarised using Kaplan Meier plots. The treatment effect will be evaluated using a Cox regression model. The Hazard Ratio (HR) for the treatment effect and corresponding 95% confidence interval will be presented. A

HR of less than 1 indicates a benefit of Montelukast in reducing the time to first event.

first hospital admission

first hospital attendance (A&E)

first GP visit

first episode of wheeze

Binary outcomes will be analysed with logistic regression

proportion receiving no steroids (OCS) vs. any during the trial

Proportion starting steroids (ICS) during the trial

Assumption checks and actions to be taken is assumptions do not hold

The assumption of proportional hazards for the cox regression model will be checked using the methods proposed by Grambsch and Therneau. If this assumption is violated, alternative methods will be used.

See section 8.4 for Poisson regression assumption checks.

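### Diary counts of wheeze, colds and days wheezing use follow-up time as exposure although the diary ends when IMP is stopped, so on the plain reading unrecorded months count as event-free

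*SAP*

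**What the plan says.** **The count model.** The SAP's Primary analysis section specifies a Poisson model with the "follow up time of each individual fitted as an exposure variable" and a random effect for the child. Under Secondary analysis, "The primary analysis will be repeated for each of the following secondary outcomes", and the list that follows includes the number of wheeze episodes and of OCS courses. Footnote 1 of Appendix Table 4 puts wheeze episodes, cold episodes and days wheezing under the same model, with "a random effect for individual to account for overdispersion with follow up time fitted as the exposure". Footnote 1 of Table 6 repeats this for OCS courses.

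**The source of the data.** Under Outcome measures, wheeze and cold episodes are counted "as recorded on the diary card". The number of OCS courses is also defined from diary cards.

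**When observation ends.** Derived and computed variables sets two different ends. For medical attendance, children without an event are "censored at exactly 12 months of follow up or the point of withdrawal from follow up". For cold and wheeze, children without an episode are censored at 12 months or "withdrawal from medication, as diary cards are not completed for those not taking IMP".

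**Stopping treatment is not the same as leaving.** The Withdrawals data items distinguish withdrawal from treatment from withdrawal from the trial and record a date. Table 2 gives the two kinds separate columns.

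**The concern.** An exposure term corrects for incomplete observation only if it measures the time in which events could have been recorded. For telephone outcomes, trial follow-up time does that. For diary outcomes it does not once the child has stopped IMP, because by the SAP's own statement there is then no diary. Numerator and denominator cover different periods, and the unrecorded months enter the model as months without wheeze or colds.

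The same diary cards would also be given two different times at risk: time to first wheeze or cold (Table 5) stops at withdrawal from medication for a child without an episode, while the number of wheezes or colds (Table 4) is spread over all of follow-up.

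The missing-data section relies in part on having follow-up time in the model as its reason not to impute. For the diary counts that reason fails if the exposure is the wrong length.

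The absolute rates of several secondary outcomes are at stake, and their rate ratios too if time off IMP differs by arm. Perceived lack of efficacy, poor adherence and adverse events are all listed reasons for withdrawal, and each could plausibly differ by arm.

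**Working it through.** **Is there a figure to reproduce?** No. The SAP gives no number of children who stopped IMP but stayed in follow-up. Its missing-data figures (full 12-month data on 1134 of 1347) describe the telephone data and cannot stand in for the diary. The sizes below are therefore assumptions.

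**Formula.** Let a share *s* of an arm stop IMP but remain in follow-up, and let *f* be the fraction of the year left unrecorded for those children. If stopping is unrelated to the episode rate, the recorded rate per unit of follow-up time is the true rate × (1 − *s f*). With M for montelukast and P for placebo,

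apparent IRR = true IRR × (1 − *s*M *f*M) / (1 − *s*P *f*P).

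**Mid-year stopping (*f* = 0.5), true IRR = 1**

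| *s*M vs *s*P | Calculation | Apparent IRR |
|---|---|---|
| 20% vs 20% | 0.900 / 0.900 | 1.00 (both rates 10% too low) |
| 5% vs 10% | 0.975 / 0.950 | 1.03 |
| 5% vs 15% | 0.975 / 0.925 | 1.05 |
| 10% vs 20% | 0.950 / 0.900 | 1.06 |
| 5% vs 25% | 0.975 / 0.875 | 1.11 |

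Reversing an imbalance inverts the ratio. If stopping is earlier (*f* = 0.75), 10% vs 20% gives 0.925 / 0.850 = 1.09.

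**What drives the bias.** It is the unrecorded time per arm, *s* × *f*, and not the number of withdrawals alone. With 10% stopping at *f* = 0.75 and 15% stopping at *f* = 0.5, both products are 0.075 and the IRR is 1.00.

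**With a true effect.** For illustration, take the 33% reduction from the sample size section (IRR 0.67). With 10% vs 20% and *f* = 0.5, the apparent IRR is 0.67 × 0.950 / 0.900 = 0.71.

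**Simulation check.** Overdispersed (gamma-Poisson) counts were simulated under no effect with 650 children per arm, 200 runs, an assumed 3 episodes a year and dispersion 1.

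| Stopping, *f* = 0.5 | IRR and rejection rate, follow-up time | IRR and rejection rate, diary time |
|---|---|---|
| 20% vs 20% | 1.00; 5.0% | 1.00; 4.5% |
| 10% vs 20% | 1.05; 13.5% | 0.99; 5.0% |

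With 200 runs, the Monte Carlo standard error of the 13.5% is √(0.135 × 0.865 / 200) = 2.4 percentage points. The rejection rates depend on the assumed mean and dispersion. Stopping was simulated as unrelated to the episode rate, so the check does not show that diary time cures informative stopping.

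**The case against.** The strongest reply is that the SAP never defines follow-up time for diary outcomes. Derived and computed variables shows that its authors knew when the diary ends, and that section leaves derived variables to be documented in the analysis programs. The code may therefore cut the exposure correctly. This stands in part: it is not certain that whole follow-up time will be used. But the censoring rule is worded only for children without an episode, the count models refer to the primary model and to a single follow-up time, and the data collection section speaks of wheeze days over the follow-up period. The plain reading conflicts with the diary rule, and nothing in the text resolves it.

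A reader might also infer more than the document supports:

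- *All medication counts are affected.* Salbutamol is not part of this point. Footnote 1 of Table 6 marks only puffs per episode, where unrecorded months remove episodes as well as puffs; total puffs per year has no stated model. OCS courses are defined from diary cards, but Derived and computed variables counts a medicine as used if either the diary or the telephone record shows it, so some use after stopping may be captured.
- *The intention-to-treat heading is wrong.* The SAP states that "Analysis of all primary and secondary outcomes will be performed on an intention-to-treat basis" and defines that population as everyone randomised, in the allocated group. This says who is analysed, not for how long an outcome is observed, so the heading is consistent with its definition.
- *The treatment effect is biased whenever withdrawals differ.* Only a difference in unrecorded time does this, and the SAP gives no evidence of one.
- *The primary result is in doubt.* The primary outcome and the attendance breakdown come solely from telephone data.

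**Conclusion.** The point holds for the counts of wheeze episodes, cold episodes and days wheezing, and with the stated qualification for OCS courses. Read plainly, the plan counts months without a diary as months without events. Each arm's rate is then understated by the fraction *s* × *f*. The IRR is unaffected if that fraction is equal between arms and shifted if it is not.

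The size is unknown. Under the assumed mid-year stopping of 5% versus 10% up to 5% versus 25%, the IRR under no effect is 1.03 to 1.11, and the inverse if the imbalance runs the other way. More placebo children stopping would hide a benefit of montelukast; more montelukast children stopping would create an apparent one. These figures assume that stopping is unrelated to the episode rate.

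This should be corrected before the analysis. It concerns secondary outcomes and does not threaten the primary conclusion.

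**What to change.** 1. For wheeze episodes, cold episodes and days wheezing, fit as exposure the days from randomisation to the earliest of withdrawal from medication, withdrawal from the trial, or 12 months. This extends the SAP's own censoring rule, and the withdrawal date is already collected.
2. Keep trial follow-up time for telephone outcomes.
3. For OCS courses, state which record the count comes from and match the exposure to it: diary time if counted from diary cards only. If telephone reports are also counted, say how the exposure covers the period without a diary.
4. Report diary exposure time per arm in Tables 4 and 6, and note there that diary outcomes are observed only while the child is on IMP. The intention-to-treat heading can stay.
5. Add a sensitivity analysis for informative stopping, for example one that lets the unrecorded episode rate after stopping differ from the recorded rate by a range of factors, separately by arm.

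The cost is one derived variable, revised footnotes and one sensitivity analysis. The diary outcomes will show less person-time. Shortening the exposure aligns events with observation but still assumes that stopping IMP is unrelated to the episode rate, so item 5 is needed as well.
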